6 STUDY PROCEDURES

[REDACTED]

[REDACTED]

[REDACTED]

[REDACTED]

[REDACTED]

[REDACTED] y and informed consent
has been obtained, the subject will be enrolled in the study.
The first treatment may occur on the same day as the screening procedures.

[REDACTED]

[REDACTED]

[REDACTED]

[REDACTED]

[REDACTED]

[REDACTED]

[REDACTED]

7 ADVERSE EVENTS AND ADVERSE DEVICE EVENTS

The image consists of a series of horizontal black bars of varying lengths and positions, set against a white background. The bars are irregular in shape, with some having sharp ends and others being more rounded. They are positioned in a way that suggests they are redacting text or obscuring specific information. The overall effect is one of a heavily redacted or abstracted document.

[REDACTED]

[REDACTED]

[REDACTED]

e.

[REDACTED]

[REDACTED]

7.2 Recording AEs/ADEs and SAEs/SADEs

All AEs/SAEs or ADEs/SADEs will be: (1) evaluated and must be recorded in the subject's study case report forms (CRFs); (2) monitored and tracked from the time of the first treatment.

At each contact with the subject, the investigator must seek information on AEs/ADEs/SADEs by specific questioning and, as appropriate, by examination. AEs/ADEs/SADEs may be observed by the investigator and/or clinical research staff, elicited from the subject and/or family member or volunteered by the subject. All observed and volunteered adverse signs and symptoms, anticipated or unanticipated, regardless of severity or frequency, will be recorded in the case histories (medical chart and CRFs). Included in the description should be the nature of the sign or symptom, the date of onset, date of resolution (duration), the severity, anticipated or unanticipated, the relationship to study treatment or other therapy, the action taken (if any), and the outcome.

All SAEs/SADEs, anticipated or unanticipated, must be reported to Cutera immediately but not later than 5 working days. The SADE must be recorded in: (1) the CRF and (2) a written report must be submitted to Cutera within five (5) working days after the investigator first learns of the event and is to include a full description of the event and sequelae, in the format detailed by the Cutera Serious Adverse Event Form

7.3 Follow-up of Subjects after AEs

All reported AEs/ADEs/SAEs/SADEs should be followed until resolution or until the subject's participation in the study ends. Resolutions of AEs/ADEs/SAEs/SADEs are to be documented on the appropriate CRFs. All ADEs that result in permanent discontinuation from this clinical trial, whether serious or not, should also be reported on the subject Non-Completion of Study Form.

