5.2.1 Subject Discontinuation Criteria

If possible, every subject should remain in the study until completion of the required follow-up period. However, participation in this study is completely voluntary and a subject can choose to withdraw from the study at any time. Decision to withdraw will not affect or prejudice the subject's continued medical care in any way. In those instances, the investigator will attempt to obtain a final clinical assessment and an adverse device effect evaluation for the subject prior to this withdrawal. A subject will be considered lost to follow-up only after three unsuccessful, documented attempts to contact the subject have been made.

In addition, a subject can be discontinued for any of the following reasons: the Principal Investigator decides that continuing in the study would not be in the subject's best interest, a subject is noncompliant with the protocol, a subject has a serious reaction to the treatment, a subject develops any of the exclusion criteria during the study period or the study is stopped by the study sponsor.

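### Follow-up of adverse events stops when participation ends, and a serious reaction may end participation, so the later course of a reaction still open at exit can go unrecorded

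*Protocol*

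**What the plan says.** Section 7.3 sets one end point for following all events, serious and device-related ones included: they "should be followed until resolution or until the subject's participation in the study ends". It makes no exception for events still open and refers to no other section. For "All ADEs that result in permanent discontinuation from this clinical trial, whether serious or not", it adds one step, an entry on the non-completion form.

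Section 5.2.1 first deals with voluntary withdrawal, where "the investigator will attempt to obtain a final clinical assessment and an adverse device effect evaluation for the subject prior to this withdrawal". It then continues: "In addition, a subject can be discontinued for any of the following reasons". One of those reasons is that "a subject has a serious reaction to the treatment". The section opens with a general wish that subjects stay to the end of follow-up where possible.

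Section 7.2 lists what each event description should hold, including "the date of onset, date of resolution (duration), the severity, anticipated or unanticipated" and also "the action taken (if any), and the outcome". For serious adverse device effects it requires a written report within "five (5) working days after the investigator first learns of the event and is to include a full description of the event and sequelae".

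Section 4.1.1 makes the incidence and severity of adverse device events the safety endpoint, and section 4.3.2 grades severity from 1 to 3. Section 9.2 restricts the analysis sets to enrolled subjects who finish treatment. Section 9.4 counts each adverse event term once per subject; where the same event recurs in a subject, it uses the worst severity and the longest duration.

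**The concern.** The event that removes a subject from the trial can also end the duty to follow that event. A reaction that is unresolved when the subject is discontinued is highly relevant to the safety of the device, yet 7.3 closes the record at that moment. If the reaction later worsens, resolves or leaves a lasting effect, no legible rule asks anyone to record it. This is a matter of data collection, so it cannot be left to the analysis: no later method recovers observations that were never made.

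**Working it through.** No calculation applies, because the protocol gives neither an expected number of such exits nor their timing. The check sets the sections side by side.

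**Does the gap exist?**

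1. The follow-up duty ends at resolution or at the end of participation, whichever applies (7.3).
2. Participation can end because of a serious reaction (5.2.1), and 7.3 expects some device events, serious or not, to end participation in the trial. The legible text does not separate stopping treatment from leaving the study.
3. If the event is open at that point, step 1 ends the duty to follow it. No legible text extends it.

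**Do other provisions close it?**

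| Provision | What it secures | What it leaves open |
|---|---|---|
| Exit evaluation, 5.2.1 | One attempted assessment before the subject leaves | Worded for voluntary withdrawal and placed before the list of other reasons, so it only arguably covers them; nothing after exit on either reading |
| Written report, 7.2 | Description and sequelae known within 5 working days of first learning of the event | Covers serious device effects only; the readable text names no later update, and the form is not shown |
| Questioning at each contact, 7.2 | Recording of what is learned when contact occurs | Creates no duty to make contact after exit |
| General wish to retain subjects, 5.2.1 | Follow-up where possible | The reasons for discontinuation follow as exceptions |

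**What does the gap affect?**

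- Incidence: unaffected for the open event, which was already recorded before exit.
- Severity: an event graded 1 or 2 at exit that worsens later keeps its exit grade. An event already at 3 cannot move, because 3 is the top of the scale.
- Resolution date and final outcome: not part of the endpoint, but required by 7.2 for each event.
- Duration in 9.4: used only when a subject reports the same event more than once, so the effect on that table is confined to that case.

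**Would better follow-up reach the tables?** This depends on when the subject leaves.

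- Exit after finishing treatment, before the last follow-up: the subject is in the 9.2 set, and later worsening would reach the 9.4 tabulation.
- Exit before finishing treatment: read literally, 9.2 leaves the subject out, so neither the event nor its later course would be tabulated. Changing 7.3 alone would not help here.

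**Which time point could bound extra follow-up?** Section 4 refers to follow-up 12 weeks after final treatment, while section 4.1.2 lists an assessment 12 weeks after both the first and the final treatment. For someone who leaves between treatments, a bare reference to the planned 12-week visit would therefore be ambiguous. Counting from the last treatment received removes the ambiguity.

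**The case against.** The strongest reply is that nothing here conflicts. Section 5.2.1 permits discontinuation without requiring it, 7.3 states a clear end point, and both can be obeyed. That is right. A reader might infer a contradiction between 5.2.1, 7.2 and 7.3, but the text does not support one; the weakness is in what the rules produce when combined.

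A reader might also infer that serious reactions go unreported. They do not: 7.2 requires recording of all events and a prompt report of serious ones, and what is seen up to exit is kept.

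The link to the endpoint is thin. It needs an event below grade 3 at exit that worsens afterwards and, as 9.2 stands, a subject who had finished treatment. This objection stands and limits the weight of the point. It also shows that 9.2 needs attention alongside 7.3.

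Sections 6 and 7.1 are redacted and the study schedule in Appendix 1 cannot be read, so a rule for open events may exist there. This cannot be excluded. It does not remove the point, because 7.3 is the section on follow-up after adverse events, is legible, and states its end point without qualification or cross-reference.

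Finally, this is a descriptive pilot with no formal testing (section 9.3). That makes the consequence smaller, but safety is one of its stated objectives and the data at issue are safety data.

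**Conclusion.** The point holds as a minor one. Followed as written, 7.3 and 5.2.1 together allow a reaction still open at discontinuation to go without recorded worsening after exit, resolution date or final outcome, although 7.2 asks for severity, resolution date and outcome. Only worsening after exit, from grade 1 or 2, bears on the safety endpoint.

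No size of loss can be given, and any percentage would be invented. The conclusion rests on two assumptions: that discontinuation under 5.2.1 ends participation in the sense of 7.3, and that no redacted or unreadable text already provides for open events.

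**What to change.** All changes concern data collection and tabulation only:

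1. **Section 7.3.** For subjects discontinued by the investigator or because of an adverse event who have not withdrawn consent, continue recording open events by visit or phone until resolution or 12 weeks after the last treatment received, whichever comes first, while the study is open.
2. **Section 5.2.1.** State that the attempted exit evaluation of adverse device effects applies to every type of discontinuation.
3. **Section 9.2.** State that the safety tabulation in 9.4 includes all treated subjects, so that those removed for a reaction before finishing treatment are not left out.

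If a redacted section already provides item 1 or 2, a cross-reference from 7.3 or 5.2.1 is enough.

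The cost is a short amendment, with IRB approval before use as section 10.3.1 requires, and a few extra contacts with discontinued subjects who have an open event. Who is discontinued, and how subjects are treated, does not change. Events still open at the 12-week limit would remain without a later outcome, as they do now for subjects who complete the study.

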8 POTENTIAL RISKS / BENEFITS

8.2 Potential Benefits

The subjects may or may not benefit from the treatment with the study device. Potential benefit is improved appearance of treated area. There is no guarantee of success.

9 DATA ANALYSIS PLAN

9.1 Sample Size

This is an exploratory pilot study and 60 subjects has been deemed appropriate for evaluation of the device.

9.2 Analysis Sets

The analysis sets will include all enrolled subjects who complete treatment.

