4.1 Study Endpoints

4.1.1 Safety Endpoint

- Incidence and severity of adverse device events.

4.1.2 [REDACTED] Endpoints

- [REDACTED]
- [REDACTED].
- GAIS at 12 weeks post first and final treatment from Baseline.
- [REDACTED]
- [REDACTED]
- [REDACTED].

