9.4 Safety Analyses

Device-related and procedure-related adverse effects (AEs) will be tabulated and analyzed. For a given AE term, counting will be done by subject, not by event, i.e. for a subject reporting the same AE more than once, the event will be counted only once, at the most severe and longest duration. The number and percentage of subjects experiencing each AE Term will be descriptively summarized.

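### As written, section 9.2 confines every analysis set, with no exception for safety, to subjects who complete treatment, so a subject stopped early by a device reaction drops out of the safety tables

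*Protocol*

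**What the plan says.** Section 9.2 consists of one sentence: "The analysis sets will include all enrolled subjects who complete treatment". It speaks of sets in the plural, gives them a single membership rule and mentions no separate safety population.

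Section 9.4 describes the safety tables: "The number and percentage of subjects experiencing each AE Term will be descriptively summarized". For a subject who reports the same term more than once, "the event will be counted only once, at the most severe and longest duration". It names no denominator.

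Four other sections bear on who is affected:

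- Section 5.2.1 lists among the reasons for discontinuing a subject that "a subject has a serious reaction to the treatment, a subject develops any of the exclusion criteria during the study period". For subjects who withdraw, it asks the investigator to "attempt to obtain a final clinical assessment and an adverse device effect evaluation for the subject prior to this withdrawal".
- Section 7.3 provides for "All ADEs that result in permanent discontinuation from this clinical trial, whether serious or not" and sends these to a non-completion form.
- Section 7.2 requires adverse events to be "monitored and tracked from the time of the first treatment".
- Section 4.1.2 includes the endpoint "GAIS at 12 weeks post first and final treatment from Baseline", so more than one treatment is possible for at least some subjects.

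**The concern.** The safety endpoint in section 4.1.1 is how often adverse device events occur and how severe they are. Under 9.2, membership of the analysis set depends on that same outcome: a reaction bad enough to end treatment early removes the subject who had it. The events lost are therefore the treatment-ending ones, which a safety table most needs to show.

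Three things follow:

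- Treatment-ending events are under-counted.
- Because 9.4 enters each subject at the worst grade and longest duration, those grades and durations are lost as well.
- Subjects who fail to complete for unrelated reasons leave the denominator, so the percentage for a given term is neither the all-treated rate nor a figure biased in a known direction.

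Section 9.3 plans no formal testing, so the descriptive table is the safety result. Safety is a stated objective (section 3), and the synopsis lists its endpoint apart from the exploratory ones.

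**Working it through.** **Which rule governs the safety tables.** Section 9.4 specifies counts and percentages of subjects but no population. Section 9.2 is the only place in the readable text that defines one, so it supplies both numerator and denominator.

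**Who is removed.** The case needs a subject who is treated, reacts and does not complete treatment. Section 4.1.2 shows that a first and a final treatment can differ. Sections 5.2.1 and 7.3 allow stopping because of a reaction. Sections 7.2 and 5.2.1 mean that the subject's events are on record. Subjects whose event does not stop treatment, or begins after the last treatment, stay in the set and are unaffected.

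**Illustration of size.** The plan gives no figure to reproduce: section 9.1 sets 60 subjects without a calculation, and no reaction or dropout rate is stated. I take N = 60 from section 9.1 and assume that all are treated. Every event and dropout count below is assumed.

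Let x be the number of treated subjects with a given adverse event term, d the number of those who stop before completing, and e the number of subjects free of that event who also fail to complete.

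- All-treated rate: x/N
- Rate under 9.2: (x − d)/(N − d − e)
- Exact (Clopper-Pearson) 95% limits for k of n: the lower limit is the 0.025 quantile of Beta(k, n − k + 1) and the upper limit is the 0.975 quantile of Beta(k + 1, n − k). For k = 0 the lower limit is 0.

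With no other dropouts (e = 0):

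| x | d | All treated (95% CI) | Under 9.2 (95% CI) |
|---|---|---|---|
| 2 | 2 | 2/60 = 3.3% (0.4% to 11.5%) | 0/58 = 0% (0% to 6.2%) |
| 6 | 2 | 6/60 = 10.0% (3.8% to 20.5%) | 4/58 = 6.9% (1.9% to 16.7%) |
| 6 | 3 | 6/60 = 10.0% (3.8% to 20.5%) | 3/57 = 5.3% (1.1% to 14.6%) |
| 6 | 6 | 6/60 = 10.0% (3.8% to 20.5%) | 0/54 = 0% (0% to 6.6%) |

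**Direction of the percentage.** Setting (x − d)/(N − d − e) = x/N and solving for e gives the break-even number of event-free dropouts:

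e = d(N/x − 1)

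- x = 6, d = 1: e = 1 × (60/6 − 1) = 9, giving 5/50 = 10.0%, unchanged.
- x = 6, d = 2: e = 2 × (60/6 − 1) = 18, giving 4/40 = 10.0%, unchanged.
- x = 6, d = 1, e = 12: 5/47 = 10.6% (3.6% to 23.1%), higher than the all-treated rate.

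Below the break-even number the percentage is too low; above it, too high. The count x − d is too low whenever d > 0. If every case of a term ends treatment early (d = x), the table shows zero whatever the other dropouts.

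**Chance that it happens at all.** If each subject's risk p of being stopped by a reaction before completing were known, the chance of losing at least one of 60 would be 1 − (1 − p)^60. For assumed p of 1%, 2% and 5% this is 45%, 70% and 95%.

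**The case against.** The best counter-argument is about reach. The number of treatments is redacted in section 4, section 6 is almost wholly blacked out, and what counts as completing treatment may be defined there. Section 4.2 puts participation at about three months and follow-up is at 12 weeks, which leaves little room for a long course. If a single session completes treatment for most subjects, only those whose session is cut short are lost. Section 7.3 concerns leaving the trial rather than stopping treatment, and the reasons in 5.2.1 can also arise during follow-up, when the subject has already completed treatment and stays in the set. Section 9.2 does not mention safety by name. The study is a pilot with no formal tests and no visible decision threshold. Subjects are protected in any case: serious events go to the sponsor within 5 working days, and the data could be re-tabulated later.

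Most of this stands as a limit on size. The number of subjects affected cannot be known from the document and may be small or nil. The break-even examples need 10 or 20 of 60 subjects not completing, and nothing in the document suggests that.

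It does not remove the defect. Sections 5.2.1 and 7.3 need only allow a reaction before completion, and they do. Even with one planned session, a session halted for a reaction could count as not completed. Nor is this a detail left to a statistical analysis plan: the protocol states a rule, and a plan that used all treated subjects would depart from it. Expedited reporting protects subjects but does not correct the published table.

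**Conclusion.** The concern holds: the rule in 9.2 is wrong as written for the safety analysis. Followed literally, it leaves treated subjects whose reaction ended treatment early out of the incidence and severity tables. That safety falls under the rule is inferred from the plural wording of 9.2 and the silence of 9.4, but it is the direct reading and nothing visible contradicts it.

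The size is unknown. On the assumed counts, an event seen in 2 of 60 treated subjects can vanish from the table, and a 10.0% rate can be shown as anything from 0% to slightly above 10%, depending on who else fails to complete. The count of subjects with a treatment-ending event can only be understated; the net percentage can move either way. It should be corrected before analysis because it affects the one visible endpoint that the synopsis does not label exploratory.

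**What to change.** In section 9.2, define a safety set of all subjects in whom device treatment was started at least once, whether or not they completed it. In section 9.4, name that set as numerator and denominator for every table, and add a listing of subjects who discontinued because of an adverse device event. The completer set may stay for the exploratory endpoints if it is labelled as a completer analysis.

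The cost is one sentence in 9.2, a named denominator and a listing in 9.4, and the signatures and IRB approval that section 10.3.1 requires for an amendment. No new data are needed, because events are already recorded from the first treatment. The only downside is that the reported safety figures may look slightly less favourable.

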9.3 Analysis of Efficacy/Exploratory Endpoints

Formal hypothesis testing and statistical analysis are not planned for this study.

9.4 Safety Analyses

Device-related and procedure-related adverse effects (AEs) will be tabulated and analyzed. For a given AE term, counting will be done by subject, not by event, i.e. for a subject reporting the same AE more than once, the event will be counted only once, at the most severe and longest duration. The number and percentage of subjects experiencing each AE Term will be descriptively summarized.

10 STUDY MANAGEMENT AND ADMINISTRATIVE PROCEDURES

[REDACTED]

[REDACTED]

[REDACTED]

[REDACTED]

[REDACTED]

[REDACTED]

[REDACTED]

10.3 Protocol Compliance

The principal investigator must comply with all terms of the protocol.

10.3.1 Protocol Amendments

Neither the principal investigator nor the sponsor will modify or alter this protocol without first obtaining the concurrence of the other party (with the exception of amendments which involves mitigating a medical emergency or immediate health risk to the subject). The party initiating an amendment must confirm it clearly in writing and it must be signed and dated by the sponsor and the principal investigator. IRB approval must be obtained before implementation of an amendment.

10.3.2 Protocol Deviations

All protocol deviations must be clearly described on the case report form (i.e., Cutera Protocol Deviation Form). Deviations from the protocol may include but are not limited to subject's failure to attend scheduled visit during a visit window, and incomplete or incorrect study procedures. Any medical emergency or immediate health risk to the subject which results in a protocol deviation and must be reported to the sponsor within 5 working days

[figure not shown]
[figure not shown]
Significant protocol deviations must be reported to IRB according to their policies.

[REDACTED]

[REDACTED]

10.5 Subject Confidentiality

This study preserves the confidentiality of all subjects under the Health Insurance Portability and Accountability Act of 1996 (HIPAA) Privacy Rule. The following safeguards will be in place to protect the privacy of the individuals who are the subjects of the health information to be used in the research and the confidentiality of that information:

[figure not shown]

